## 7.3 Permitted Therapy

Use of any permitted medication, including over-the-counter medications or vaccine during the 28 days prior to first injection through Week 28 or Early Discontinuation Visit should be solicited from each subject and recorded in source documents. Use of vitamins and dietary supplements will not be collected unless they are indicated as a concomitant therapy for conditions directly related to undergoing hemodialysis. Medications started prior to first dose, and any medication used in the 28 days prior to first dose but not continued at the time of first dose, will be recorded.

All collected concomitant medications will be recorded in the electronic Case Report Form (eCRF) through Week 28. After Week 28, only prescription medication or over-the-counter drug taken by the subject for the treatment of MAEs, SAEs, AMIs, or AESIs will be recorded on the

eCRF through EOS Visit (further details regarding safety monitoring of AMIs and AESIs are provided in Section [9.4.7.2](#)).

## **8.0 MANAGEMENT OF STUDY TREATMENT TOXICITIES**

### **8.1 Reasons for Stopping a Subject From Receiving Additional Injections**

The investigator will discontinue study treatment and notify the sponsor if any of the following MAEs occur:

- Grade 4 post-injection reaction within 7 days after any study injection
- Clinically significant Grade 3 or higher systemic reaction (eg, angioedema, generalized urticaria) within 7 days after any study injection
- Grade 3 or 4 hypotension within 24 hours of any study injection
- Grade 3 or 4 respiratory reaction or symptoms occurring within 24 hours of any study injection
- Any life-threatening event, regardless of relationship to study drug
- Any AMI (further details regarding safety monitoring of AMIs are provided in Section [9.4.7.2](#))
- Any confirmed AESI (further details regarding safety monitoring of AESIs are provided in Section [9.4.7.2](#))

Subjects must also be discontinued from study treatment for any of the following reasons:

- Violation of protocol eligibility criteria
- Prohibited medications
- SAE assessed as a suspected adverse reaction (SAR) or adverse reaction (AR)
- Pregnancy or breastfeeding

Subjects may be discontinued from the study for any of the following reasons:

- Violation of protocol eligibility criteria (only if the subject has not received any study treatment)
- Prohibited medications (only if the subject has not received any study treatment)
- Noncompliance with study procedures as determined by the investigator or sponsor
- The discretion of the investigator

- The sponsor's administrative decision to terminate the study

The investigator or designee must notify Dynavax within 24 hours when a subject has been discontinued from treatment due to an MAE. The subject should not be withdrawn from the study and should continue to be followed for safety (as defined in Section 9.7) through EOS Visit.

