## **9.5 End of Study**

An EOS Visit is required at Week 68 unless the subject is discontinued early from the entire study, in which case an Early Discontinuation Visit is required 28 days after the last dose.

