## **9.7 Duration of Follow-up**

All subjects must be followed through EOS Visit (Section 10.0). If the subject is discontinued early from study treatment, the subject should not be withdrawn from the study and should continue to be followed for safety through EOS Visit. If the subject is discontinued early from the study, an Early Discontinuation Visit is required 28 days after the last dose.

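### Section 8.1 lets injected subjects be taken out of the study for noncompliance or at the investigator's discretion, an unbounded exception to follow-up through EOS that may understate the primary safety proportions

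*Protocol*

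**What the plan says.** Protocol Section 8.1 separates stopping injections from leaving the study. The second list opens "Subjects may be discontinued from the study for any of the following reasons". Its first two reasons, eligibility violation and prohibited medication, are restricted to subjects not yet injected, as in "Prohibited medications (only if the subject has not received any study treatment". The next two are "Noncompliance with study procedures as determined by the investigator or sponsor" and "The discretion of the investigator". Neither has that restriction, and the discretion reason has no criterion at all. Noncompliance may be determined by the sponsor as well as by the investigator.

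On follow-up, Section 9.7 states "All subjects must be followed through EOS Visit", then adds "If the subject is discontinued early from the study, an Early Discontinuation Visit is required 28 days after the last dose". Section 9.5 has the matching exception: "An EOS Visit is required at Week 68 unless the subject is discontinued early from the entire study". Sections 8.3 and 9.6 also tie the closing visit to the last injection, while the Appendix 1 footnote allows it at 28 days or later. Subjects who only stop injections stay under safety follow-up to EOS (Sections 7.2, 8.1, 9.4.7, 9.6 and 9.7).

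The primary safety endpoints (Protocol Section 4.2.1, SAP Section 4.0) are proportions of subjects with treatment-emergent MAEs; with SAEs, AMIs or deaths; and with AESIs. SAP Section 7.1 runs the treatment-emergent period from first injection to the EOS visit. SAP Section 7.2 divides by the number in the analysis population and leaves missing safety data unimputed. SAP Section 9.7 plans counts and percentages, Section 9.8 plans nothing further, and Section 9.1 tabulates study discontinuations with their reasons.

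**The concern.** Elsewhere the protocol takes care to keep an injected subject under safety observation after injections stop. The two unrestricted reasons leave a way around that intention. A subject removed through either one has a single closing visit and then no Week 28, 42 or 68 contact, apart from any that came before removal.

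At analysis the subject stays in the safety denominator and the unobserved weeks add nothing to the numerator, so they count as event-free. This lowers the proportion even when removed subjects are at only average risk. It lowers it further if missed visits or a clinician's decision to withdraw reflect poor health, which is plausible in hemodialysis patients but not documented here. Safety is the first-listed primary objective, and there is no control arm in which the same loss could be seen. Events that are never collected also cannot enter the AMI and AESI counts used by the study-termination criteria in Section 8.2.

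**Working it through.** **Scale taken from the plan.** Enrolment is about 115, which is 100 × 1.15. The expected 15% loss before Week 20 is 0.15 × 115 = 17.25, about 17 subjects. Table 11-1 reproduces by Clopper-Pearson: 90 of 100 gives 82.4% to 95.1%, width 0.127. The point does not depend on that table; it serves below as a yardstick of precision.

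**Observation lost per removed subject.** Follow-up runs from Day 1 to Day 477, so 477 − 1 = 476 days. Injections are on Days 1, 29, 57 and 113. With close-out exactly 28 days after the last one:

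| Last dose | Close-out day | Days observed | Share lost |
|---|---|---|---|
| 1 | 29 | 28 | 1 − 28/476 = 94% |
| 2 | 57 | 56 | 1 − 56/476 = 88% |
| 3 | 85 | 84 | 1 − 84/476 = 82% |
| 4 | 141 | 140 | 1 − 140/476 = 71% |

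A later closing visit loses less.

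**Effect on a reported proportion.** The documents give neither a removal rate nor event risks in removed subjects, so these are assumptions: N = 115; k subjects removed, with k from 3 to 17 (the top being the plan's whole expected loss); constant hazard; observation ending on Day 141. If the 68-week risk in removed subjects is p, the part seen is 1 − (1 − p)^(140/476), and the understatement is (k/115) × (p − part seen).

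At p = 10%, the same as in retained subjects, the part seen is 1 − 0.9^0.294 = 3.05%, a gap of 6.95 points. For k = 17 this is 17/115 × 6.95 = 1.03 points. Results in percentage points at average hazard:

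| 68-week risk | k = 3 | k = 6 | k = 12 | k = 17 |
|---|---|---|---|---|
| 5% | 0.09 | 0.18 | 0.37 | 0.52 |
| 10% | 0.18 | 0.36 | 0.73 | 1.03 |
| 46% | 0.77 | 1.54 | 3.07 | 4.35 |

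The 46% row only illustrates a common event. It equals the 13-month MAE proportion in Study 3 of the package insert in Appendix 2, which was not a hemodialysis population.

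**Two sensitivities at 10% risk in retained subjects.**

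- Threefold risk in removed subjects: p = 30%, part seen 1 − 0.7^0.294 = 9.96%, gap 20.04 points. The understatement is 0.52 points at k = 3 and 2.96 at k = 17.
- All close-outs after dose 1, average hazard: part seen 1 − 0.9^(28/476) = 0.62%, gap 9.38 points. For k = 17 the understatement is 17/115 × 9.38 = 1.39 points.

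**The case against.** A reader might infer that Section 8.1 flatly contradicts Section 9.7. It does not. Sections 9.5 and 9.7 expressly foresee early discontinuation from the study, so this is a rule with a stated exception. What remains is that two of the grounds for the exception have no bound.

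A reader might also infer that sicker subjects are selectively lost. No passage links removal to risk, and several close the illness-driven routes. Subjects stopped for an MAE stay in follow-up, SAEs judged possibly or probably related are followed beyond EOS, and AESIs are followed until resolved, chronic or stable. Nor is a subject who misses an injection through a long hospital stay a clear example. Stopping injections alone does not end follow-up, and an in-patient stay for a new or worsening illness already counts once in the MAE endpoint and once in the SAE, AMI or death endpoint. For that subject only the AESI proportion and the separate AMI and death tabulations could still miss an event. This stands. It limits the harm mainly to subjects with no qualifying event before removal, and to AESIs, AMIs and deaths.

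Third, the 15% expected loss cannot be read as a removal rate. It is loss to follow-up before Week 20, and the documents do not say how much, if any, would come through these two reasons. The Appendix 1 footnote also allows a later closing visit, so the 71% to 94% range applies only to close-out at 28 days.

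Finally, the study is descriptive, discontinuations are tabulated with reasons, and a 1-point shift is small beside an interval width of about 12.7 points for 10 of 100 (by symmetry with the 90% row of Table 11-1). This is fair context. But a disposition table shows how many left without recovering their events, and a downward bias remains however wide the interval.

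**Conclusion.** The point holds as an unbounded exception with a one-directional effect. As written, injected subjects can be removed for noncompliance (by investigator or sponsor) or at the investigator's discretion. Close-out at 28 days leaves 71% to 94% of the safety period unobserved, and the SAP's denominator and missing-data rules count that time as event-free. Safety proportions may therefore be understated even without selection, and by more if removal tracks illness.

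The size is unknown because the documents give no removal rate. The illustration of about 0.2 to 1.0 points rests on 10% risk, average and constant hazard, close-out on Day 141 and 3 to 17 removals among 115. It is smaller for rarer events or later close-out, and larger for common events, earlier close-out or higher risk in removed subjects. A direct contradiction, demonstrated selective loss, or a specific percentage of avoidable loss would go beyond what the documents support. The change is still worth making, because it recovers primary outcome data at little cost.

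**What to change.** - **Protocol Sections 8.1 and 9.7:** reconcile them by stating that injected subjects are not removed from safety follow-up for noncompliance or at investigator discretion. MAE, SAE, AMI, AESI and vital-status data continue to be collected at the existing Week 28, 42 and 68 contacts, with Week 68 by telephone if needed, unless the subject withdraws consent. The rules for stopping injections stay as they are.
- **SAP Section 9.7:** add an exposure-adjusted or time-to-event summary of the primary safety endpoints, with censoring at last contact, to account for subjects with incomplete follow-up. This corrects for shorter observation but not for removal related to illness; only continued data collection addresses that.

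The cost is a short protocol change and one added SAP summary. Weeks 28 and 42 are already telephone contacts. The small downside is that sites keep contacting subjects they would otherwise have closed out.

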## **8.2 Potential Reasons for Termination of Study**

The study will terminate on the date of the last visit of the last participant. However, the sponsor reserves the right to terminate the study at any time. Reasons for termination include but are not limited to:

- Inability to enroll sufficient subjects into the study
- Federal regulations/Good Clinical Practice (GCP) compliance issues that compromise the validity of the study and/or subject safety
- AMIs occurring in  $\geq 10\%$  of subjects AND occurring in  $\geq 4$  subjects (further details regarding safety monitoring of AMIs are provided in Section 9.4.7.2)
- AESIs occurring in  $\geq 5\%$  subjects AND occurring in  $\geq 3$  subjects (further details regarding safety monitoring of AESIs are provided in Section 9.4.7.2)

## **8.3 Management of Subject Safety**

Subjects will be evaluated prior to each study injection to confirm the subject is eligible (per eligibility criteria [Section 5.0], as relevant) to receive an injection.

Injection-site reactions are expected to spontaneously subside. Local pruritus and pain can be treated with oral medications. If significant symptoms of pain and induration persist for more than 12 hours, an ice pack may be applied locally for 30 minutes every 2 hours, as needed. Use of an ice pack prior to 12 hours after the onset of symptoms is discouraged, as it may interfere with the action of the study vaccine. Do not inject into a site if local pain, tenderness, swelling, or pruritus persists from a previous injection or other cause.

Subjects should receive appropriate supportive care measures as deemed necessary by the investigator. The investigator should ensure that adequate medical care is provided to a subject for any MAE, including clinically significant laboratory values, related to the study. For each disorder, attempts should be made to rule out other causes, which might require additional supportive care. The investigator should inform the study medical monitor when medical care is needed for intercurrent illness(es) of which the investigator becomes aware.

An unscheduled visit (UNS) should be performed if there are suspected subject safety concerns. All supportive therapies will be recorded in the subject's eCRF.

Subjects who are discontinued from the study will be scheduled for an Early Discontinuation Visit 28 days following their last vaccine administration.

## **9.0 STUDY PROCEDURES**

All tests and evaluations required at specified time points are listed in the Schedule of Assessments ([Appendix 1](#)). The results of these tests and evaluations must be entered in the subject's source document and also recorded on the subject's eCRF. Additional evaluations may be done at the discretion of the investigator and with sponsor approval.

### **9.1 Informed Consent, Screening, and Eligibility**

#### **9.1.1 Informed Consent and Screening**

The investigator or designee must review the informed consent form (ICF) with each prospective subject to be certain that the prospective subject understands the procedures and risks of the study. Prospective subjects who wish to participate in the study must provide written informed consent by signing the ICF before undergoing any screening procedures. Subjects may undergo study screening tests prior to giving written informed consent provided that these tests are considered part of standard care.

The information from the consent form should be translated and communicated to the subject in language understandable to the subject.

A copy of the signed and dated consent form should be given to the subject before participation in the study. The initial ICF and any subsequent revised written ICF, and written information must receive the Institutional Review Board/Independent Ethics Committee (IRB/IEC) approval/favorable opinion in advance of use. The subject or his/her legally acceptable representative should be informed in a timely manner if new information becomes available that may be relevant to the subject's willingness to continue participation in the study. The communication of this information should be documented.

The investigator or designee will maintain a log of all subjects who sign the ICF. At a minimum, the log will include a subject identifier, the dates of informed consent and screening procedures, the outcome of the screening, and the reason the subject did not enroll in the study, if applicable.

For screen failures, at a minimum age, sex, ethnicity, race, height, and weight, the reason for screen failure, and any SAEs that occur during the screening period will be collected.

Additional requirements for informed consent are presented in Section [13.3](#).

### **9.1.2 Eligibility**

After written consent is obtained, screening procedures must be carried out per the Schedule of Assessments ([Appendix 1](#)). A subject must meet all of the inclusion criteria and none of the exclusion criteria to be eligible to participate in the study. Documentation of ESRD must be obtained prior to enrollment. Assignment of subject number is described in the Study Reference Manual.

### **9.1.3 Demographics and Medical and Medication History**

Demographic and baseline characteristics of sex, race, ethnicity, age, weight, and height of the subject will be collected. Medical history, defined in Section [9.4.1](#), will also be recorded.

## **9.2 Study Visits**

Procedures should be performed as close to the scheduled time as possible. The window for study visits is  $\pm$  7 days. A detailed outline of all scheduled study procedures is provided in the Schedule of Assessments ([Appendix 1](#)). Procedures should be performed at the study center where the subject is being treated, except for Weeks 28 and 42 which will be conducted via telephone call. Subjects who fail screening may be rescreened per approval by the sponsor.

The exact time at which a procedure is performed must be recorded in the subject's study records or appropriate worksheet (if applicable). Any nonscheduled procedures required for urgent evaluation of safety concerns take precedence over all routine scheduled procedures.

Blood collections for safety evaluation assume priority over other procedures. Laboratory samples must be collected prior to HEPLISAV-B administration on study injection visit days. Blood collection and HEPLISAV-B administration must be performed prior to the start of dialysis on study visit days.

## **9.3 Immunogenicity Assessments**

Serum sample will be obtained for anti-HBs measurements at baseline and then at Weeks 4, 8, 16, and 20.

## **9.4 Safety Assessments**

The safety assessments are listed below. The Schedule of Assessments is provided in [Appendix 1](#).

#### **9.4.1 Medical and Medication History**

Medical history includes clinically significant diseases, surgeries, kidney disease history, autoimmune diseases, and all medications (eg, prescription drugs, over-the-counter drugs) used by the subject within 28 days prior to the Screening Visit.

#### **9.4.2 Physical Examinations**

The investigator or qualified designee will conduct physical examinations. A full physical examination (excluding pelvic/genital, rectal, and breast examination) will be conducted at Screening, and a targeted physical examination based on subject-reported symptoms (excluding pelvic/genital, rectal, and breast examination) will be conducted at each study injection visit and End-of-Study (EOS) Visit or Early Discontinuation Visit.

#### **9.4.3 Safety Laboratory Assessments**

Laboratory assessments are listed below and will be performed according to the Schedule of Study Assessments ([Appendix 1](#)). Sample collections will be prior to injection on vaccination days. Laboratories obtained within 7 days of Day 1 visit do not need to be repeated on Day 1.

- Serum chemistry and hematology will be performed at Screening by a central laboratory.
- Hepatitis and HIV testing at Screening Visit by a central laboratory: serum hepatitis B, hepatitis C, and HIV testing by laboratory tests for HBsAg, anti-HBc, anti-HBs, anti-HCV, and anti-HIV-1/2, respectively
- Reserve serum and plasma aliquot specimens will be collected and stored frozen for possible future testing.
- Additional details for specific tests are provided in the Laboratory Manual.

#### **9.4.4 Pregnancy Testing**

All WOCBP (as defined in Section [5.2.1](#)) who are being considered for participation in the study will be tested for pregnancy with a serum test at Screening Visit and a serum or urine  $\beta$ -human chorionic gonadotropin ( $\beta$ -hCG) test within 72 hours prior to taking each dose of study treatment. If the urine test is positive or cannot be confirmed as negative, then a serum test is required which must be negative for the subject to enroll.

#### **9.4.5 Confirmation of Subject Eligibility**

Subjects will be evaluated prior to each study injection to confirm the subject is eligible (per eligibility criteria [Section [5.0](#)], as relevant) to receive an injection.

#### **9.4.6 Post-injection Reaction Assessments**

Assessments of post-injection reactions will be collected for a minimum of 30 minutes following each of the HEPLISAV-B injections at the clinical site and as reported by the subject in a diary for 7 days. Information about the presence and severity of post-injection local (injection site) reactions (redness, swelling, and pain at or near the injection site) and systemic reactions (malaise, headache, myalgia, and fatigue) that are listed in the subject diary are considered solicited post-injection reactions. Oral temperature is also collected. Solicited post-injection reactions are related to treatment and recorded for 7 days following each study injection, including the day of injection. Post-injection reactions documented by the subject will be collected, reviewed by the study nurse/coordinator with the subject, and recorded on the appropriate eCRF. The grading criteria for post-injection reactions are in [Appendix 3](#). Further information is provided in the Study Reference Manual.

#### **9.4.7 Medically-Attended Adverse Events**

All MAEs, as defined in Section [10.2](#), will be evaluated from immediately after the first study treatment on Day 1 through EOS Visit. (Additionally, if the subject is discontinued early from study treatment, the subject should not be withdrawn from the study and should continue to be followed for safety, as described in Section [9.7](#), through EOS Visit.)

##### **9.4.7.1 Adverse Events of Special Interest**

Subjects who experience signs or symptoms that the investigator or designee considers to be associated with potential AESIs (defined according to a pre-specified list of event terms including autoimmune, autoinflammatory, and hypersensitivity disorders; Appendix 4 provides the full list), as well as any other potentially immune-mediated medical conditions that do not appear in Appendix 4, will be referred for consultation with appropriate experts (eg, rheumatology, immunology) for confirmation.

###### **9.4.7.1.1 Adverse Events of Special Interest Reporting Requirements**

All potential AESIs, regardless of seriousness, severity, or relationship to the injection, will be reported to Dynavax or the Dynavax designee. In addition to describing the event on the appropriate eCRFs and in the source documents, Dynavax should be informed within 72 hours by contacting the Dynavax Medical Monitor or designee by submitting a completed Potential Autoimmune Event Report Form (events assessed as serious must be reported to Dynavax or its designee within 24 hours of investigator awareness of the event, as described in Section [10.3.2](#)). Follow-up information should be actively sought and submitted as it becomes available.

Any AESI regardless of relationship to study treatment will be followed as clinically indicated until its resolution or, if non-resolving, until it is considered chronic or stable by the investigator.

Once the site principal investigator refers a subject to an expert evaluation for possible AESI, injections should be discontinued until further notice. If the expert evaluation reveals that the subject did NOT have an AESI, injections can be resumed. If the expert evaluation confirms an AESI, then injections will be permanently discontinued for the subject. In either event, the subject will be followed for safety (as defined in Section 9.7) through EOS Visit.

